11 ADVERSE EXPERIENCE REPORTING AND DOCUMENTATION

11.1 Adverse Events

An adverse event (AE) is any untoward medical occurrence in a clinical investigation of a patient administered a pharmaceutical product and that does not necessarily have a causal

PI: [name]

relationship with the treatment. An AE is therefore any unfavorable and unintended sign (including an abnormal laboratory finding), symptom or disease temporally associated with the administration of an investigational product, whether or not related to that investigational product.

The Investigator and Independent Medical Monitor will probe, via discussion with the patient's clinical providers, for the occurrence of AEs during the patient visit and record the information in the site's source documents. Adverse events will be recorded in the patient CRF. Adverse events will be described by duration (start and stop dates and times), severity, outcome, treatment and relation to study drug, or if unrelated, the cause.

AE Severity

The National Cancer Institute's Common Terminology Criteria for Adverse Events (CTCAE) Version 3.0 will be used to assess and grade AE severity, including laboratory abnormalities judged to be clinically significant. The guidelines shown in Table 1 below will be used to grade severity. It should be pointed out that the term "severe" is a measure of intensity and that a severe AE is not necessarily serious.

Table 1. AE Severity Grading

Severity (Toxicity Grade)	Description
Mild (1)	Transient or mild discomfort; no limitation in activity; no medical intervention or therapy required. The patient may be aware of the sign or symptom but tolerates it reasonably well.
Moderate (2)	Mild to moderate limitation in activity, no or minimal medical intervention/therapy required.
Severe (3)	Marked limitation in activity, medical intervention/therapy required, hospitalizations possible.
Life-threatening (4)	The patient is at risk of death due to the adverse experience as it occurred. This does not refer to an experience that hypothetically might have caused death if it were more severe.

AE Relationship to Study Drug

The relationship of an AE to the study drug should be assessed using the following the guidelines in Table 2.

Table 2. AE Relationship to Study Drug

Relationship to Drug	Comment
Definitely	Previously known toxicity of agent; or an event that follows a reasonable temporal sequence from administration of the drug; that follows a known or expected response pattern to the suspected drug; that is confirmed by stopping or reducing the dosage of the drug; and that is not explained by any other reasonable hypothesis.
Probably	An event that follows a reasonable temporal sequence from administration of the drug; that follows a known or expected response pattern to the suspected drug; that is confirmed by stopping or reducing the dosage of the drug; and that is unlikely to be explained by the known characteristics of the patient's clinical state or by other interventions.
Possibly	An event that follows a reasonable temporal sequence from administration of the drug; that follows a known or expected response pattern to that suspected drug; but that could readily have been produced by a number of other factors.
Unrelated	An event that can be determined with certainty to have no relationship to the study drug.

11.2 Serious Adverse Experiences (SAE)

An SAE is defined as any AE occurring at any dose that results in any of the following outcomes:

- death
- a life-threatening adverse experience
- inpatient hospitalization or prolongation of existing hospitalization
- a persistent or significant disability/incapacity
- a congenital anomaly/birth defect

Other important medical events may also be considered an SAE when, based on appropriate medical judgment, they jeopardize the patient or require intervention to prevent one of the outcomes listed.

PI: [name]

11.2.1 Serious Adverse Experience Reporting

Study site will document all SAEs that occur (whether or not related to study drug) per [UCLA OHRPP Guidelines](#). The collection period for all SAEs will begin after admission and end after discharge.

In accordance with the standard operating procedures and policies of the Institutional Review Board, the site investigator will report SAEs to the IRB.

11.3 Protocol Defined Important Medical Findings Requiring Real Time Reporting

The following additional event is to be reported in real time to the IRB and FDA:

Hemolytic transfusion reactions: Defined as a clinical syndrome within 24 hours of blood transfusion including one or more symptoms (back pain, shortness of breath, hematuria, chills, dizziness, fever, urticaria) with clinical or laboratory evidence of hemolysis (hematuria, decreased haptoglobin, increased lactate dehydrogenase or bilirubin, or positive direct antigen test). Requires immediate cessation of ongoing blood transfusion and reporting as SAE.

11.4 Medical Monitoring

The Sponsor/Investigator, as well as the Independent Medical Monitor, will monitor for adverse effects and should be contacted directly to report medical concerns or questions regarding safety: Medical monitor ([name]) [contact] e-mail: [contact]

12 DISCONTINUATION AND REPLACEMENT OF PATIENTS

12.1 Early Discontinuation of Study Drug

A patient may be discontinued from study treatment at any time if the patient, or Sponsor/Investigator feels that it is not in the patient's best interest to continue. The following is a list of possible reasons for study treatment discontinuation:

- Hemolytic transfusion reaction
- Adverse event that in the opinion of the Sponsor/Investigator would be in the best interest of the patient to discontinue study treatment
- Protocol violation requiring discontinuation of study treatment

PI: [name]

If a patient is withdrawn from treatment due to an adverse event, the patient will be followed and treated by the Sponsor/Investigator until the abnormal parameter or symptom has resolved or stabilized.

12.3 Withdrawal of Patients from the Study

A patient may be withdrawn from the study at any time if the patient or the Sponsor/Investigator feels that it is not in the patient's best interest to continue.

All patients are free to withdraw from participation at any time, for any reason, specified or unspecified, and without prejudice.

Reasonable attempts will be made by the Sponsor/Investigator to provide a reason for patient withdrawals. The reason for the patient's withdrawal from the study will be specified in the patient's source documents.

12.4 Replacement of Patients

Patients who withdraw from the study will be replaced.

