4 STUDY DESIGN

4.1 Study Overview

This is a single center, prospective cohort study. Enrollment of approximately 98 patients is planned, 49 receiving whole blood and 49 receiving component therapy. This is an observational study planned during initiation of a change in practice at our institution initially allowing up to 4 units of whole blood transfusion for adult male trauma patients. If initial patients receiving whole blood show no evidence of hemolysis and thrombocytopenia compared to patients receiving component therapy, up to 6 units of whole blood transfusion will be allowed (see below, and section 5.2, Safety Evaluations). Patients in the whole blood, or index, group are adult male trauma patients presenting in hemorrhagic shock (systolic blood pressure < 100) requiring massive transfusion activation who receive whole blood for resuscitation. Two control groups will be utilized. The prospective control group consists of adult male patients who present during times when whole blood is not available, as well as adult female patients, presenting in hemorrhagic shock (systolic blood pressure <100) requiring massive transfusion activation. Additionally, a second control group consisting of historical

PI: [name]

controls receiving component therapy will be analyzed (see Section 6, Patient Selection, for details of index and control groups).

All patients will have, in addition to standard labs, additional labs drawn for thromboelastography, platelet function determination, and coagulation factor levels (see Section 9.1.6, Other Clinical Procedures, for details of specific lab tests and timing).

Patients who meet all inclusion criteria and none of the exclusion criteria will be enrolled into the study.

Total duration of patient participation will be approximately 1 year (365 days), or the duration of the hospital stay, whichever is shorter. This includes up to 5 days of laboratory testing during initial resuscitation and subsequent admission, and up to one year of follow up via chart review if the patient remains in the hospital. Total duration of the study including recruitment and follow up is expected to be 2 years.

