8.2 Blinding

The study is not blinded.

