9 STUDY PROCEDURES AND GUIDELINES

A Schedule of Events representing the required testing procedures to be performed for the duration of the study is diagrammed in Appendix 1.

Due to the emergent nature of treatment, and the fact that both whole blood and component therapy are considered standard of care for traumatic resuscitation of adult males, the UCLA Institutional Review Board has waived the requirement for informed

PI: [name]

consent and Health Insurance Portability and Accountability Act (HIPAA) authorization. As an FDA approved product, whole blood is not considered an investigational treatment by the Institutional Review Board and therefore these requirements have been waived for the entire study. Patients will be informed of which product they received and of the study by their clinical providers, but not directly by study personnel.

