13 PROTOCOL VIOLATIONS

A protocol violation occurs when the patient or Sponsor/Investigator fails to adhere to significant protocol requirements affecting the inclusion, exclusion, patient safety and primary endpoint criteria. Protocol violations for this study include, but are not limited to, the following:

- Failure to meet inclusion/exclusion criteria
- Switching from component therapy to whole blood

Failure to comply with Good Clinical Practice (GCP) guidelines will also result in a protocol violation. The Sponsor/Investigator will determine if a protocol violation will result in withdrawal of a patient.

When a protocol violation occurs, it will be discussed with the Sponsor/Investigator and a Protocol Violation Form detailing the violation will be generated. This form will be signed by a Sponsor/Investigator or representative. A copy of the form will be filed in the site's regulatory binder and in the Sponsor/Investigator's files.

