15.1 Data Sets Analyzed

All eligible patients who are enrolled in the study and receive at least one unit of blood, and who undergo TEG testing as described above, will be included in analysis.

Data sets include:

PI: [name]

1. Prospectively identified patients who received whole blood or component therapy and did not have severe TBI
2. Prospectively identified patients who received whole blood or component therapy and who had severe TBI (GCS 8 or less with evidence of brain injury on imaging)
3. Prospectively identified patients who received whole blood or component therapy, all patients regardless of TBI status
4. Prospectively identified male patients who received whole blood and who did not have severe TBI, compared to historical control male patients who received component therapy and who did not have severe TBI

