15.3 Analysis of Primary Endpoint

Primary analysis compares volume of blood products transfused in the first 24 hours of admission in patients without severe TBI (severe TBI is defined as GCS \leq 8 and evidence of brain injury on imaging) receiving whole blood versus component therapy during initial resuscitation.

For continuous variables including the primary endpoint, the statistical method will depend on the distribution of the data. If the data appears to follow a normal distribution, a t-test will be used, otherwise, a nonparametric Wilcoxon rank sum test will be used.

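### The withdrawal, replacement and TEG rules permit selection of patients after the 24-hour volume is known, and the direction of any bias cannot be foreseen

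*Protocol*

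**What the plan says.** - **Blinding (8.2):** "The study is not blinded".
- **Withdrawal (12.3):** "A patient may be withdrawn from the study at any time if the patient or the Sponsor/Investigator feels" that continuing is not in the patient's best interest. The same section lets patients leave freely and asks that the reason be recorded in source documents.
- **Protocol violations (13):** "The Sponsor/Investigator will determine if a protocol violation will result in withdrawal of a patient". One of the two violations listed by name is a switch from component therapy to whole blood.
- **Replacement (12.4):** "Patients who withdraw from the study will be replaced". No limit is set on reason, timing or number.
- **Primary outcome (15.3):** "volume of blood products transfused in the first 24 hours of admission in patients without severe TBI".
- **Length of participation (4.1):** "Total duration of patient participation will be approximately 1 year (365 days), or the duration of the hospital stay, whichever is shorter".
- **Consent (9):** this is waived. "Patients will be informed of which product they received and of the study by their clinical providers, but not directly by study personnel".
- **Analysis set (15.1):** "All eligible patients who are enrolled in the study and receive at least one unit of blood, and who undergo TEG testing as described above". The section does not mention withdrawn patients.
- **Enrolment (6.2):** the plan is to include every eligible patient who presents over about two years.

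**The concern.** The primary outcome is complete one day after admission, but a patient can be withdrawn until discharge or day 365. Most of the withdrawal window therefore opens once the volume is known, to an investigator who also knows the product given. Because consent is waived and patients hear of the study from their clinicians, a patient's own withdrawal may also come after the outcome.

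If a withdrawn patient leaves the analysis and a new one takes the place, the compared groups depend in part on decisions made after treatment. The groups are not randomised and the primary analysis has only about 31 patients per group, so a few such decisions matter. The TEG condition adds a second post-treatment filter to an outcome, transfused volume, that does not need TEG to be measured.

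**Working it through.** **1. The plan's own figure.** Section 15.5 expects about 18 of 49 per group to have severe TBI: 49 - 18 = 31, and 31 / (1 - 18/49) = 49. This reproduces. Over the stated 35-40% range, 49 × 0.65 = 31.9 and 49 × 0.60 = 29.4. The 80% power cannot be reproduced, because no numerical effect size or SD is given. Solved backwards at two-sided alpha 0.05, the standardised difference is (1.960 + 0.842) × √(2/31) = 0.71 SD. The point does not rest on this figure.

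**2. Can withdrawal follow the outcome?** The outcome closes at 24 hours (15.3). Participation lasts to discharge, typically about 14 days (10.1), or to day 365 (4.1). Sections 12.3 and 13 set no earlier cut-off. So it can.

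**3. Does a withdrawn patient still count?** Section 15.1 does not say. TEG as described earlier in the protocol is drawn on admission, after every six units, at 3 and 6 hours, at hemostasis and on ICU days 1, 3 and 5 (9.1.6). If the condition means any TEG, most patients withdrawn after 24 hours still qualify. If it means the full series, a withdrawal before ICU day 5 removes the patient. Under 6.2 all eligible presenters are enrolled anyway, so it is unclear where a replacement would come from.

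**4. Size in a worst case.** Assumptions, none of them from the protocol: no true difference; 31 per group; lognormal volumes; the k highest-volume patients of one group are removed and replaced by random new patients. The test is two-sided Wilcoxon at 0.05, one of the two tests that 15.3 allows. It uses ranks only, so its error rates do not depend on the log SD. Results from 20,000 simulated trials, with removal from the whole blood group:

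| k replaced | Any false finding | False finding in favour of that group (lower volume) | Difference: false finding against it |
|---|---|---|---|
| 0 | 4.95% | 2.50% | 2.45% |
| 1 | 5.85% | 4.13% | 1.72% |
| 2 | 7.22% | 6.25% | 0.97% |
| 3 | 9.93% | 9.24% | 0.69% |

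A longer check of 100,000 trials gave 8.8% and 0.8% at k = 3. With the t-test on the same lognormal data (log SD 1), the false finding in favour at k = 3 is about 16%.

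The ratio of mean volumes does depend on the assumed log SD. For 0.7 to 1.0 it falls to 0.92-0.86 (k = 1), 0.87-0.78 (k = 2) and 0.83-0.73 (k = 3). On normal data the shift at k = 3 is 0.16 SD, and 0.16 / 0.71 = 23% of the difference that 31 per group can detect with 80% power.

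**5. Direction.** The table is symmetric in the two groups. If the patients removed come from the component group, its last column becomes the false rate of lower volume on whole blood: 2.45% falls to 0.69%. The named violation, a switch from components to whole blood, can arise only in patients who started on components, whom 6.2 places in the component group. If such patients tend to need more blood, which the protocol does not show, withdrawing them works against whole blood.

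**The case against.** A reader might infer that these rules tilt the trial towards whole blood. The documents do not support that. The one concrete trigger they name acts on the component group and could push the other way. The 9% figure needs selection driven wholly by outcome and confined to the whole blood group, and nothing in the protocol suggests that this is intended. Withdrawals unrelated to volume would not bias the comparison.

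Other points stand in part:

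- Section 12.4 speaks of patients who withdraw, which may cover only those who leave by their own choice. But it follows directly on 12.3, which covers both kinds and does not separate them.
- Section 15.1 can be read as keeping anyone who had a unit of blood and some TEG. On that reading little bias arises and replacement only adds patients. The text does not say so.
- Withdrawal must rest on the patient's best interest, with the reason recorded. Violations need a signed form, and an independent medical monitor reviews clinical data. These make selection visible; they do not prevent it.
- A reader might also infer that replacement serves no purpose because outcomes come from the chart. That is wrong: the TEG and hemolysis endpoints need blood draws, so a patient lost before sampling does cost information.
- The handling of withdrawn patients is often left to the SAP. But replacement and the TEG condition are rules that this protocol states, and an SAP written before the final analysis may come after patients have been withdrawn and replaced.

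**Conclusion.** The concern holds as a statement of what the text permits. Sections 12.3, 12.4, 13 and 15.1 together allow patients to leave the primary comparison after their outcome is known and others to take their place, and they do not fit the consecutive enrolment planned in 6.2. It cannot be said that selection will occur, or which group it would favour.

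In the worst case, with 3 of 31 replaced and a Wilcoxon test, the false rate of lower volume on whole blood is about 9% if whole blood patients are removed and 0.7-0.8% if component patients are, against 2.5% nominal. Both figures assume no true effect and removal strictly by highest volume. The protocol gives neither a withdrawal rate nor an SD with which to judge how near the trial would come to either. The point should be corrected, since the remedy is cheap and removes the ambiguity whichever reading was meant.

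**What to change.** 1. In 15.1, state that every eligible enrolled patient who received at least one unit stays in the primary volume analysis, in the group of the first product given, regardless of later withdrawal, protocol violation or TEG completion. Data are kept as the IRB waiver allows. The severe-TBI exclusion is unchanged.
2. Limit the TEG condition to the TEG endpoints.
3. Delete 12.4, or amend it so that any additional patient supplements the withdrawn one and never removes that patient, and say how this fits 6.2.
4. Report withdrawals and protocol violations by arm, with reasons.

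The cost is wording only, and the target of 49 per group does not change. The downside is that a few patients in the primary analysis may have incomplete TEG or hemolysis data, which affects those secondary endpoints and not the volume comparison.

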12.5 Stopping Criteria

Pre-specified stopping criteria are as follows:

1. Hemolytic transfusion reaction: Defined as a clinical syndrome within 24 hours of blood transfusion including one or more symptoms (back pain, shortness of breath, hematuria, chills, dizziness, fever, urticaria) with clinical or laboratory evidence of hemolysis (hematuria, decreased haptoglobin, increased lactate dehydrogenase or bilirubin, or positive direct antigen test). Requires immediate cessation of ongoing blood transfusion and reporting as SAE. As this is an unexpected and serious event, any hemolytic transfusion reaction following the administration of whole blood will prompt temporary cessation of the study while the event is evaluated. If the event indeed occurred after administration of low titer group O-positive whole blood, the study will be stopped.

2. Additionally, interim analysis will seek evidence for increased incidence of clinical coagulopathy, increased transfusion requirements, and increased incidence of complications as defined above in Secondary Endpoints, or increased mortality, all of which will prompt stopping the study.

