
SECONDARY ENDPOINTS
	
 1. Volume of blood transfusion within 24 hours of admission for patients with severe TBI (GCS \leq8 and evidence of brain injury on imaging) and for entire cohort of patients. 2. Thromboelastography parameters including maximum amplitude, reaction time, alpha angle, fibrinolysis, and platelet function at 3 and 6 hours of resuscitation, after every 6 units of whole blood equivalent (WB or PRBCs), at the time of completion of resuscitation (time of last unit of blood product given), and on ICU days 1, 3 and 5. 3. 30-day mortality; 4. Duration of need for renal replacement therapy, mechanical ventilation, ICU admission, and hospital stay; 5. Number of units of blood products transfused by component/product during first 24 hours of admission and total for hospitalization; 6. Complications which include 30-day mortality, clinical coagulopathy, infection, venous thromboembolism, cerebrovascular accident, acute coronary syndrome, transfusion-related lung injury, transfusion-associated cardiac overload; 7. Hemolysis as measured by haptoglobin, bilirubin, lactate dehydrogenase, and direct antiglobulin 8. Wastage of blood units

SAFETY EVALUATIONS
	
Complications which include death, clinical coagulopathy, infection, venous thromboembolism, cerebrovascular accident, acute coronary syndrome, transfusion-related lung injury, transfusion-associated cardiac overload;
 
Hemolysis as measured by haptoglobin, bilirubin, lactate

	dehydrogenase, and direct antiglobulin.
PLANNED INTERIM ANALYSES	When approximately 50% of patients have been enrolled in the study, an interim analysis for safety will be conducted by the statistician and independent medical monitor. Serious adverse events will be monitored by the medical monitor on an ongoing basis throughout the study.

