5 CRITERIA FOR EVALUATION

5.1 Primary Efficacy Endpoint

The primary objective is to assess the clinical efficacy of whole blood compared to component therapy for trauma patients requiring massive transfusion. Primary analysis will compare volume of blood transfusion within 24 hours of admission for patients without severe TBI (defined as GCS \leq 8 and imaging evidence of brain injury) for patients who received WB versus component therapy for initial resuscitation.

Secondary Efficacy Endpoints

The secondary objectives will evaluate the effect on survival; the development of multiple complications related to survival; and wastage data. The full list of secondary endpoints is as follows:

1. Volume of blood transfusion within 24 hours of admission for patients with severe TBI (GCS \leq 8 and imaging evidence of brain injury) and for entire cohort of patients.
2. Thromboelastography parameters including maximum amplitude, reaction time, alpha angle, fibrinolysis, and platelet function at 3 and 6 hours of resuscitation, after every 6 units of whole blood equivalent (WB or PRBCs) given, at the time of completion of resuscitation (time of last unit of blood product given), and on ICU days 1, 3 and 5.
3. 30-day mortality;

PI: [name]

4. Duration of need for renal replacement therapy, mechanical ventilation, ICU admission, and hospital stay;
5. Number of units of blood products transfused by component/product during first 24 hours of admission and total hospitalization;
6. Complications which include clinical coagulopathy, infection, venous thromboembolism, cerebrovascular accident, acute coronary syndrome, transfusion-related lung injury, transfusion-associated cardiac overload during total hospitalization;
7. Hemolysis as measured by haptoglobin, bilirubin, lactate dehydrogenase, and direct antiglobulin on ICU day 1;
8. Wastage of blood units

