- The incidence of adverse events will be evaluated including: death, clinical coagulopathy, hemolysis, infection, venous thromboembolism, cerebrovascular accident, acute coronary syndrome, transfusion-related lung injury, transfusion-associated cardiac overload.
- The occurrence of any whole blood transfusion given to patients other than adult male trauma patients will also be recorded
- In addition to ongoing monitoring and final analysis, an interim safety analysis when approximately 50% of patients have been enrolled will determine if there is a difference in adverse events as defined above between groups.
- The interim analysis will be performed by the independent medical monitor. The independent medical monitor, [name], is an emergency medicine physician with extensive experience in clinical investigation and has no relation to the study other than to monitor safety. The independent medical monitor has the authority to stop the study if safety concerns arise, including but not limited to evidence for the pre-specified stopping criteria (see Section 12.5, Stopping Criteria). [name] is also independent of the Blood and Blood Derivatives Committee.

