15.5 Interim Analysis

When approximately 50% of patients have been enrolled in the study, an interim analysis for safety is planned to be conducted by the independent medical monitor. (See Section 5.2, Safety Evaluations).

Sample Size

Number of patients to be enrolled was calculated using a Type I error rate of 0.05, and effect size based on reduction of PRBC and plasma transfusions described in the sensitivity analysis in a study by Cotton et al. ¹

As in the sensitivity analysis by Cotton et al, patients with severe TBI (defined as TBI on imaging with GCS of 8 or less) will be excluded from primary analysis. Approximately 35-40% of patients meeting inclusion criteria are expected to fulfill criteria for severe TBI. It is not possible to identify patients with severe TBI prior to beginning resuscitation for hemorrhagic shock, so all patients meeting inclusion criteria will be enrolled. In the primary analysis, only patients without severe TBI will be compared. Secondary analyses will compare 1) patients with severe TBI receiving WB versus component therapy and 2) the entire cohort of enrolled patients, with and without TBI, receiving WB versus component therapy. Using this method, a total sample size of 49 whole blood arm (study drug) and 49 component therapy arm (control) patients (98 patients total) is planned. 35-40% (approximately 18 of the total 49) of eligible patients are expected to have severe TBI and to be excluded from primary analysis based on typical presentations of trauma patients. 49 total patients per group will achieve a sample size of approximately 31 patients per arm without TBI to complete the primary analysis. The FDA will be notified in advance if sample size estimates change.

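### Must the interim stopping grounds in section 12.5, item 2, carry a written threshold and say whether the stop is mandatory?

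*Protocol*

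**What the plan says.** Protocol section 12.5 gives two stopping criteria under a heading that calls them pre-specified. Item 1 concerns a hemolytic transfusion reaction after whole blood: a temporary halt while the event is evaluated, then a final stop if it is confirmed. Item 2 reads: "Additionally, interim analysis will seek evidence for increased incidence of clinical coagulopathy, increased transfusion requirements, and increased incidence of complications", where complications are those of the secondary endpoints, and it closes "or increased mortality, all of which will prompt stopping the study".

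Section 5.2 says that the interim look at about half enrolment "will determine if there is a difference in adverse events as defined above between groups". It continues: "The independent medical monitor has the authority to stop the study if safety concerns arise", on grounds "including but not limited to evidence for the pre-specified stopping criteria (see Section 12.5, Stopping Criteria" (the quotation ends just before the closing bracket). Section 15.5 adds that "an interim analysis for safety is planned to be conducted by the independent medical monitor"; the Synopsis also names the statistician. Section 14 repeats the timing. Section 15.4 names the chi-squared test for categorical safety data, without a level for stopping.

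The secondary-endpoint list of complications appears twice. The Synopsis version begins "Complications which include 30-day mortality, clinical coagulopathy, infection, venous thromboembolism, cerebrovascular accident, acute coronary syndrome". The version under section 5.1 begins "Complications which include clinical coagulopathy, infection, venous thromboembolism, cerebrovascular accident, acute coronary syndrome, transfusion-related lung injury" and omits death, which stands there only as a separate endpoint.

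**The concern.** Three features of item 2 invite criticism. First, a criterion called pre-specified gives no size of increase, no test level and no comparator. Second, its four headings are joined by an and, then an or, then a closing phrase about all of them, so one could ask whether one heading is enough or all four are needed. Third, 12.5 words the consequence as something that will follow, whereas 5.2 speaks of authority to stop.

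The headings also overlap. Coagulopathy is a heading of its own and a listed complication, and mortality is too if the Synopsis list applies.

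The interim groups will be small, unblinded (section 8.2) and not randomised, with women only among the controls (section 6.1). If the rule meant stopping on any numerical excess, a study with no true harm would usually stop. If it meant a significant excess on every heading, it would almost never stop.

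**Working it through.** The Protocol states no false-stop rate or interim power, so there is no figure of its own to reproduce. The check sets out the possible readings, sizes each one, and then asks which reading the text supports.

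**Inputs.** Planned enrolment is 98 (section 4.1), and half of that is 49. The split at the interim is not fixed; 24/24, 24/25, 30/18 and 18/30 (whole blood/control) were tried. The Protocol gives no event rates or correlations, so these are assumptions, in a low/high set: mortality 15/25%, coagulopathy 20/40%, infection 15/25%, venous thromboembolism 5/10%, and four other complications 1/3% each. Correlation between outcomes is 0, 0.3 or 0.6. Transfusion volume is compared by rank sum. The groups are treated as exchangeable, with no true difference.

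**One heading, 24 v 24, exact binomial enumeration.** For event rates of 10-50%, whole blood shows a bare numerical excess with probability 0.40-0.44. A chi-squared excess in the harmful direction at nominal two-sided 0.05 has probability 0.024-0.030.

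**Four independent headings, for scale.** With a 20% event rate, three binary headings at 0.428 and volume at 0.5:
- any bare excess: 1 - (1 - 0.428)³ × (1 - 0.5) = 0.906;
- any excess at 0.025 per tail: 1 - (1 - 0.025)⁴ = 0.096;
- any excess at 0.05 per tail: 1 - (1 - 0.05)⁴ = 0.185.

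**Four correlated headings, simulated (20,000 replicates per setting).**

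| Reading of an increase | Chance of a flag with no true harm |
|---|---|
| Bare excess, any one heading | 75-88% at 24/24; 78-93% at the other splits |
| Bare excess, all four | 6-17% at 24/24; 8-23% at the other splits |
| Significant, any one, chi-squared | 7-11% at one-sided 0.025; 13-19% at 0.05 |
| Significant, any one, Fisher exact | 4-6% at one-sided 0.025; 9-12% at 0.05 |
| Significant, all four | below 0.4% |

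A separate normal-theory calculation, with correlations from 0 to 0.8, gives 69-94% for a bare excess on any one heading and 6-31% on all four. At 0.025 per tail on any one heading it gives 6-10%.

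**Which reading the text supports.** Section 12.5 has the interim look for evidence of an increase. Section 5.2 has it determine whether the groups differ. Section 15.4 supplies chi-squared for categorical safety comparisons. None of these describes stopping because one group has one more event, so the first two rows of the table are poor readings. After a closing or, the phrase about all of the headings most naturally means each of them, so the all-four rows are strained too. That leaves a nominal chi-squared excess on any one heading: about 7-19% across the two levels.

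**The two complications lists.** At 24/24, for a bare excess on any heading, the largest change from the section 5.1 list to the Synopsis list is 0.872 to 0.858, or 1.4 percentage points. Mortality is already a heading of its own, so adding it to the complications hardly moves the rule.

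**Sections 5.2 and 12.5 side by side.** Section 5.2 says who decides and allows grounds beyond 12.5. Section 12.5 lists particular grounds. One refers to the other, and neither calls the stop automatic. Item 1 says outright that the study will be stopped once the event is confirmed; item 2 says only that its findings prompt a stop.

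**What a formal threshold would gain.** Exact one-sided Fisher power for mortality of 40% v 20% at the four splits is 0.33, 0.34, 0.28 and 0.33 at level 0.05, and 0.48, 0.51, 0.45 and 0.45 at level 0.10. Even a doubling of mortality would be missed about half the time or more, and would then fall to the monitor's judgement in any case.

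**The case for a change.** The strongest counter-argument rests on the Protocol's own label. If criteria are called pre-specified, what triggers them should be known before the interim data are seen. Section 15 promises the SAP only before the final analysis, so it may not exist by then. Item 1 shows that the authors could define a trigger and a sequence of steps when they chose to. In an unblinded, non-randomised comparison, an unwritten threshold means that neither a stop on noise nor the dismissal of a real signal could be checked against the document.

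Part of this stands. No level is written, and the text does not settle beyond argument whether evidence under item 2 obliges a stop or informs the decision. But the date given for the SAP is a latest date; it does not show that nothing will be agreed before the interim. Test levels for a safety look are commonly left to a SAP or monitoring plan. Choosing between a mandatory stop and a documented judgement is a matter of governance for the sponsor, the IRB and the monitor, and statistical argument does not settle it.

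**Conclusion.** No change to the plan follows. The threshold for item 2 is unwritten, but sections 5.2 and 12.5 do not contradict each other. An independent monitor with authority to stop, working with the statistician, can fill the gap sensibly. On the reading nearest the text, the chance of a flag with no true harm is about 7-19%, depending on the level. The 75-93% figures belong to a bare-excess reading that the wording does not favour. The mismatch between the complications lists is editorial and moves the 24/24 any-heading result by at most 1.4 points. A formal threshold would have only 28-34% power at one-sided 0.05 for mortality of 40% v 20%, so most of the decision would still rest on judgement. All these percentages depend on assumed event rates, correlations and interim splits, and on treating non-randomised groups as exchangeable; they illustrate scale and are not bounds. The stakes are also limited: the study is observational, with both treatments described as standard of care for adult men (sections 4.1, 6.1 and 9), so a false stop would end data collection at one centre, and nothing in the Protocol says that it would change treatment.
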